5.5. Investigational Product Storage

The investigator, or an approved representative, eg, pharmacist, will ensure that all investigational product is stored in a secured area with controlled access under required storage conditions and in accordance with applicable regulatory requirements.

Investigational product should be stored in its original container and in accordance with the label. See the investigational product label for storage conditions of the product.

Storage conditions stated in the SRSD (ie, IB) will be superseded by the storage conditions stated in the labeling.

Site systems must be capable of measuring and documenting (for example, via a log), at a minimum, daily minimum and maximum temperatures for all site storage locations (as applicable, including frozen, refrigerated and/or room temperature products). This should be captured from the time of investigational product receipt throughout the study. Even for continuous monitoring systems, a log or site procedure that ensures active daily evaluation for excursions should be documented. The operation of the temperature monitoring device and storage unit (for example, refrigerator), as applicable, should be regularly inspected to ensure it is maintained in working order.

Any excursions from the product label storage conditions should be reported upon discovery. The site should actively pursue options for returning the product to the storage conditions as described in the labeling, as soon as possible. Deviations from the storage requirements, including any actions taken, must be documented and reported to the sponsor.

Once an excursion is identified, the investigational product must be quarantined and not used until the sponsor provides documentation of permission to use the investigational product. It will not be considered a protocol deviation if the sponsor approves the use of the investigational product after the temperature excursion. Use of the investigational product prior to sponsor approval will be considered a protocol deviation.

Specific details regarding information the site should report for each excursion will be provided to the site.

Receipt of materials, door opening and closing, and other routine handling operations where the product(s) are briefly out of the temperature range described in the labeling are not considered excursions. More specific details will be provided to the sites separately.

Refer to the investigational product manual for any additional guidance on storage conditions and actions to be taken when conditions are outside of the specified range.

5.6. Investigational Product Accountability

The investigative site must maintain adequate records documenting the receipt, use, loss, or other disposition of the investigational product supplies.

5.6.1. Destruction of Investigational Product Supplies

The sponsor or designee will provide guidance on the destruction of unused investigational product (eg, at the site). If destruction is authorized to take place at the study site, the investigator must ensure that the materials are destroyed in compliance with applicable environmental regulations, institutional policy, and any special instructions provided by Pfizer, and all destruction must be adequately documented.

5.7. Concomitant Treatment(s)

Concomitant treatment considered necessary for the patient's well-being may be given at the discretion of the treating physician.

All concomitant treatments, including supportive care drugs (eg, anti-emetic treatment and prophylaxis), drugs used to treat AEs or chronic disease, blood products, as well as non-drug interventions (eg, transfusions) received by patients from screening until the Follow-up visit will be recorded on the CRF.

5.7.1. Other Anti-tumor/Anti-cancer or Experimental Drugs

No additional anti-tumor treatment will be permitted while patients are receiving study treatment. Additionally, the concurrent use of select vitamins or herbal supplements is not permitted.

Palliative radiotherapy on study is permitted for the treatment of painful bony lesions provided the lesions were known at the time of study entry and the investigator clearly indicates that the need for palliative radiotherapy is not indicative of disease progression. In view of the current lack of data about the interaction of PF-06671008 with radiotherapy, PF-06671008 treatment should be interrupted during palliative radiotherapy, stopping 7 days before and resuming treatment after recovery to baseline.

5.7.2. Supportive Care

Palliative and supportive care for disease related symptoms may be administered at the investigator's discretion and according to any available American Society of Clinical Oncology (ASCO) guidelines.

5.7.3. Hematopoietic Growth Factors

Primary prophylactic use of granulocyte-colony stimulating factors is not permitted during Cycle 1, but they may be used to treat treatment emergent neutropenia as indicated by the current ASCO guidelines.

Erythropoietin may be used at the investigator's discretion for the supportive treatment of anemia.

5.7.4. Anti-Diarrheal, Anti Emetic Therapy

Primary prophylaxis of diarrhea, nausea and vomiting is not permitted in the first cycle. Primary prophylaxis in subsequent cycles is at the investigator's discretion. The choice of the prophylactic drug is up to the investigator with sponsor approval and assuming the drug is not included in the [Concomitant Treatment\(s\)](#) section, as well as the duration of treatment, assuming there is no known or expected drug-drug interaction. If so, then it must be approved by the sponsor.

5.7.5. Anti-inflammatory Therapy

Anti-inflammatory or narcotic analgesic may be offered as needed assuming there is no known or expected drug-drug interaction and assuming the drug is not included in the [Concomitant Treatment\(s\)](#) section.

5.7.6. Corticosteroids

Chronic, systemic corticosteroid use for palliative or supportive purposes is not permitted in cases other than those discussed in the [Cytokine Release Syndrome](#) section. Acute emergency administration, topical applications, inhaled sprays, eye drops, or local injections of corticosteroids are allowed.

5.7.7. Surgery

Caution is advised on theoretical grounds for any surgical procedures during the study. The appropriate interval of time between surgery and PF-06671008 required to minimize the risk of impaired wound healing and bleeding has not been determined. Stopping PF-06671008 is recommended at least 7 days prior to surgery. Postoperatively, the decision to reinitiate PF-06671008 treatment should be based on a clinical assessment of satisfactory wound healing and recovery from surgery.

6. STUDY PROCEDURES

6.1. Screening

For screening procedures see [Schedule of Activities](#) and [Assessments](#) section. Screening to be obtained within 28 days prior to registration. The informed consent document must be obtained prior to undergoing any study specific procedures. Informed consent may be obtained more than 28 days prior to registration.

6.2. Study Period

For treatment period procedures, see [Schedule of Activities](#) and [Assessments](#) section.

6.3. Follow-up Visit

For follow-up procedures see [Schedule of Activities](#) and [Assessments](#) section. The EOT assessments are to be obtained if they are not completed in the last week (last 6 weeks for tumor assessments). The Follow-Up visit should be conducted at least 28 days, and no more than 35 days, after discontinuation of treatment. Patient will return to undergo assessments per the [Schedule of Activities](#) and will be evaluated for the resolution of any

treatment-related toxicity. Patients continuing to experience toxicity at this point following discontinuation of treatment will continue to be followed at least every 4 weeks until resolution or determination, in the clinical judgment of the investigator, that no further improvement is expected. Subsequent to the Follow-Up visit, patients should be contacted by telephone every 8 weeks (± 7 days) to obtain information on subsequent anti-cancer treatment and overall survival for up to two years after randomization.

6.4. Patient Withdrawal

Patients may withdraw from treatment at any time at their own request, or they may be withdrawn at the discretion of the investigator or sponsor for safety or behavioral reasons, or the inability of the patient to comply with the protocol-required schedule of study visits or procedures at a given study site.

Reasons for withdrawal of study treatment may include:

- Objective disease progression by irRECIST (see [Appendix 5](#)). Disease progression will be confirmed with two consecutive timepoints at least 4 weeks apart in the absence of rapid clinical deterioration;
- Global deterioration of health status requiring discontinuation;
- Unacceptable toxicity;
- Pregnancy;
- Significant protocol violation;
- Lost to follow-up;
- Patient refused further treatment;
- Study terminated by sponsor;
- Death.

Reasons for withdrawal from study follow-up may include:

- Completed study follow-up;
- Study terminated by sponsor;
- Lost to follow-up;
- Refused further follow-up;
- Death.

If a patient does not return for a scheduled visit, every effort should be made to contact the patient. All attempts to contact the patient and information received during contact attempts must be documented in the patient's medical record. In any circumstance, every effort should be made to document patient outcome, if possible. The investigator should inquire about the reason for withdrawal, request that the patient return for a final visit, if applicable, and follow-up with the patient regarding any unresolved AEs.

If the patient refuses further visits, the patient should continue to be followed for survival unless the patient withdraws consent for disclosure of future information or for further contact. In this case, no further study specific evaluations should be performed, and no additional data should be collected. The sponsor may retain and continue to use any data collected before such withdrawal of consent.

7. ASSESSMENTS

Every effort should be made to ensure that the protocol-required tests and procedures are completed as described. However, it is anticipated that from time to time there may be circumstances, outside of the control of the investigator that may make it unfeasible to perform the test. In these cases the investigator will take all steps necessary to ensure the safety and well-being of the patient. When a protocol-required test cannot be performed, the investigator will document the reason for this and any corrective and preventive actions that he or she has taken to ensure that normal processes are adhered to as soon as possible. The study team will be informed of these incidents in a timely fashion.

7.1. Safety Assessment

Safety assessments will include collection of adverse events (AEs), serious adverse events (SAEs), vital signs (including pulse oximetry) and physical examination, electrocardiogram (ECG [12-lead]), laboratory assessments, including pregnancy tests and verification of concomitant treatments.

7.1.1. Pregnancy Testing

For female patients of childbearing potential, a serum or urine pregnancy test, with sensitivity of at least 25 mIU/mL and assayed in a certified laboratory, will be performed on 2 occasions prior to starting study treatment-once at the start of screening and once at C1D1, immediately before investigational product administration. Following a negative pregnancy result at screening, appropriate contraception must be commenced and a further negative pregnancy result will then be required at the baseline visit within 5 days after the first day of the menstrual period counting the first day as Day 1 before the patient may receive the investigational product. Pregnancy tests will also be routinely repeated at every cycle during the active treatment period, at the end of study treatment, and additionally whenever 1 menstrual cycle is missed or when potential pregnancy is otherwise suspected. In the case of a positive human chorionic gonadotropin (hCG) test, the patient will be withdrawn from treatment and will be withdrawn from the study. Additional pregnancy tests may also be undertaken if requested by IRB/ECs or if required by local regulations.

7.1.2. Adverse Events

Assessment of adverse events will include the type, incidence, severity (graded by the NCI CTCAE version 4.03) timing, seriousness, and relatedness.

Adverse events that occur during the study will be recorded on the adverse events CRF page.

7.1.3. Laboratory Safety Assessment

Hematology, blood chemistry, coagulation and urinalysis will be evaluated at the time points described in the [Schedule of Activities](#) and analyzed at local laboratories. There is no need to repeat the C1D1 laboratory assessments if the baseline assessment is performed within 3 days prior to dosing. Assessments performed at all subsequent dosing visits should be performed within 48 hours prior to dosing. Additional local laboratory assessments outside of the timepoints outlined in the [Schedule of Activities](#), (eg, additional local cytokine samples), may be obtained for patient safety evaluation at the discretion of the investigator.

Table 4. Laboratory Tests

Hematology	Chemistry	Coagulation	Urinalysis	Pregnancy Test	Unique Screening Labs
Hemoglobin	ALT/SGPT	PT or INR	Urine dipstick for urine protein: If positive collect 24-hr and microscopic (Reflex Testing)	For female patients of childbearing potential, serum or urine	Hepatitis B surface antigen
Platelets	AST/SGOT	PTT			Hepatitis B core antibody
WBC	Alk Phos				Hepatitis C antibody
Absolute Neutrophils	Sodium				HIV
Absolute Lymphocytes	Potassium				
Absolute Monocytes	Magnesium		Urine dipstick for urine blood: If positive collect a microscopic (Reflex Testing)		
Absolute Eosinophils	Chloride				
Absolute Basophils	Calcium				
	Total Bilirubin ¹				
	BUN or Urea				
	Creatinine				
	Uric Acid				
	Glucose (non-fasted)				
	Albumin				
	Phosphorous or Phosphate				
	LDH				
	CRP ²				

* All samples will be analyzed locally.

1. For potential Hy's Law cases, in addition to repeating AST and ALT, laboratory tests should include albumin, creatine kinase, total bilirubin, direct and indirect bilirubin, gamma-glutamyl transferase, prothrombin time (PT)/INR, alkaline phosphatase, total bile acids and acetaminophen drug and/or protein adduct levels.
2. Measurement of CRP is not required after C2D1 if within normal range or similar to baseline levels; however, CRP should be measured anytime CRS is suspected and not already scheduled to be measured (eg, Cycle 2).

7.1.4. Vital Signs and Physical Examination

Patients will have a physical examination (PE) to include vital signs, assessment of ECOG performance status and height; height will be measured at screening only. Weight will be measured at screening, the beginning of each cycle and the end of treatment. Weight does not need to be performed at each visit; however patients should be monitored throughout the study for significant weight change.

A complete PE will be performed at Screening, on Cycle 1 Day 1 and at the End of Treatment visit for each patient and will include an assessment of all body systems (including neurological examination, genitourinary examination is optional). The Cycle 1 Day 1 PE does not need to be repeated if the screening assessment is performed within 3 days of the visit. Findings of all physical examinations should be recorded in the source documents, and any change from baseline considered by the investigator to be clinically significant should be recorded as an AE in the CRF.

Abbreviated PEs should be performed as appropriate per the [Schedule of Activities](#) (SOA), and on an as needed basis for assessment of AEs. Abbreviated exams should be targeted to specific symptoms or complaints and be consistent with local standard of care.

Vital signs will include measurement of temperature (oral, tympanic, temporal or axillary), blood pressure (BP) and pulse rate to be recorded in a seated or supine position. On dosing days, vital signs should be measured prior to administration of investigational product (pre-dose) and at the end of the PF-06671008 infusion (for cohorts where PF-06671008 is administered IV). For BP assessment, the same arm (preferably the dominant arm) should be used throughout the trial. A blood pressure cuff, which has been properly sized and calibrated, should be used to measure blood pressure. The use of automated devices for measuring BP is acceptable.

On dosing days, pulse oximetry should be measured prior to administration of investigational product (pre-dose) and at the end of the PF-06671008 infusion (for cohorts where PF-06671008 is administered IV) as part of the vital sign evaluation. Pulse oximetry should be collected prior to the collection of BP and pulse rate. Oxygen levels should be evaluated on the finger in accordance with the sites standard procedures. A single reading should be collected.

7.1.5. Ophthalmic Examination

An eye exam, to be performed by an ophthalmologist, will be performed at screening. The eye exam is to include Best Corrected Visual Activity (BCVA), Intraocular Pressure (IOP) preferably by Goldmann applanation, Biomicroscopic exam (also called slit lamp exam) to evaluate the Lids/Lashes/Adnexae, conjunctiva/sclera, cornea, anterior chamber, iris, lens,

and Dilate fundus exam to evaluate the optic nerve, the vessels, the macula, and the peripheral retina. Further ophthalmic examinations should be guided by specific ocular signs and symptoms should they occur during treatment and follow up.

7.1.6. (12-Lead) Electrocardiogram

Electrocardiogram (ECG): Triplicate 12-lead (with a 10-second rhythm strip) tracing will be used for all ECGs. It is preferable that the machine used has a capacity to calculate the standard intervals automatically. At each time point (see the [Schedule of Activities](#)), 3 consecutive ECGs will be performed at approximately 2 minutes apart to determine the mean QTcF interval. If the mean QTcF is prolonged (>500 msec, ie, CTCAE Grade ≥ 3), then the ECGs should be re-evaluated by a qualified person at the site for confirmation as soon as the finding is made, including verification that the machine reading is accurate. If manual reading verifies a QTcF of >500 msec, immediate correction for reversible causes (including electrolyte abnormalities, hypoxia and concomitant medications for drugs with the potential to prolong the QTcF interval) should be performed. In addition, repeat ECGs should be immediately performed hourly for at least 3 hours until the QTcF interval falls below 500 msec. If QTcF interval reverts to less than 500 msec, and in the judgment of the investigator(s) and sponsor is determined to be due to cause(s) other than investigational product, treatment may be continued with regular ECG monitoring. If in that timeframe the QTcF intervals rise above 500 msec the investigational product will be held until the QTcF interval decreases to <500 msec. Patients will then restart the investigational product at the next lowest dose level. If the QTcF interval has still not decreased to 500 msec after 2-weeks, or if at any time a patient has a QTcF interval >515 msec or becomes symptomatic, the patient will be removed from the study. Additional triplicate ECGs may be performed as clinically indicated.

Prior to concluding that an episode of prolongation of the QTcF interval is due to investigational product, thorough consideration should be given to potential precipitating factors (eg, change in patient clinical condition, effect of concurrent medication, electrolyte disturbance) and possible evaluation by specialist.

If the patient experiences a cardiac or neurologic AE (specifically syncope, dizziness, seizures, or stroke), an ECG (triplicate) should be obtained at the time of the event.

When matched with PK sampling, the ECG must be carried out before each PK sample drawing such that the PK sample is collected at the nominal time (ie, the timing of the PK collections over rides the timing of the ECG collections).

CCI

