22. **Follow-Up:** At least 28 days, and no more than 35 days, after discontinuation of treatment, patients will return to obtain these assessments as well as evaluate the resolution of any treatment-related toxicity. Patients continuing to experience toxicity at this point following discontinuation of treatment will continue to be followed at least every 4 weeks until resolution or determination, in the clinical judgment of the investigator, that no further improvement is expected. Subsequent to the Follow-Up visit, patients should be contacted by telephone every 8 weeks (± 7 days) to obtain information on subsequent anti-cancer treatment and overall survival for up to two years from the date of randomization.

Schedule of Pharmacokinetic, CCI**Assessments for Intravenous Administration –****Cohort 1 Only**

Visit Identifier	Screen	Cycle 1												Cycle 2						Subsequent Cycles			EOT				
		1	2	4	8	24	72	0	1	2	4	8	24	72	0	1	0	1	4	24	72	0	1	0	1	0	1
Study Day																											
Hours Pre-/Post-Dose*		0	1	2	4	8	24	72	0	1	2	4	8	24	72	0	1	0	1	4	24	72	0	1	0	1	
CCI																											
Blood samples for PF-06671008		X	X	X	X	X	X	X	X	X	X	X	X	X	X	X	X	X	X	X	X	X	X	X	X	X	
Blood samples for Anti-PF-06671008 Antibody		X																									X
CCI																											
CCI																											

Schedule of Pharmacokinetic, CCI Cohort 2 and Beyond and Part 2

Assessments for Intravenous Administration – Part 1

SCHEDULE OF ACTIVITIES FOR SUBCUTANEOUS ADMINISTRATION

The schedule of activities table provides an overview of the protocol visits and procedures. Refer to the **ASSESSMENTS** section of the protocol for detailed information on each assessment required for compliance with the protocol.

The investigator may schedule visits (unplanned visits) in addition to those listed on the schedule of activities, in order to conduct evaluations or assessments required to protect the well-being of the patient.

Visit Identifier	Screen ¹ (≤28 days prior to registration)	Treatment Period										Post Treatment	
		Cycle 1 (1 cycle = 21 days)						Cycles ≥2					
		Day 1	Day 2	Day 3	Day 5	Day 8	Day 15	Day 1	Day 2	Day 8	Day 15	End of Treatment ²²	Follow-up ²³
Visit Window (days)					(±1)	(±1)	(±1)		(±2)	(±2)			
Informed consent ²	X												
Tumor history	X												
Medical history	X												
Complete physical examination	X	X ³										X	
Abbreviated physical examination					X	X	X		X	X			X
Height	X												
Weight	X	X						X				X	

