23. **Follow-Up:** At least 28 days, and no more than 35 days, after discontinuation of treatment, patients will return to obtain these assessments as well as evaluate the resolution of any treatment-related toxicity. Patients continuing to experience toxicity at this point following discontinuation of treatment will continue to be followed at least every 4 weeks until resolution or determination, in the clinical judgment of the investigator, that no further improvement is expected. Subsequent to the Follow-Up visit, patients should be contacted by telephone every 8 weeks (\pm 7 days) to obtain information on subsequent anti-cancer treatment and overall survival for up to two years from the date of randomization.

Schedule of Pharmacokinetic, CCI Assessments for Subcutaneous Administration

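### Protocol 7.1.1 (positive pregnancy test) and 7.1.6 (QTcF) take patients out of the study, while 6.3 and 6.4 keep such patients in follow-up: a low-priority wording fix

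*Protocol*

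**What the plan says.** Two safety rules in the Protocol end participation in the study.

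- Section 7.1.6 (ECG) applies if QTcF has not come down to 500 msec after 2 weeks, or if "at any time a patient has a QTcF interval >515 msec or becomes symptomatic, the patient will be removed from the study".
- Section 7.1.1 applies to a positive hCG test: "the patient will be withdrawn from treatment and will be withdrawn from the study".

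The general rules separate stopping treatment from leaving follow-up.

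- Section 6.4 has one list headed "Reasons for withdrawal of study treatment may include", which contains unacceptable toxicity and pregnancy. A second list, headed "Reasons for withdrawal from study follow-up may include", contains only completion, sponsor termination, loss to follow-up, refusal and death.
- Section 6.4 also keeps a patient who declines further visits in survival follow-up unless consent to disclosure or contact is withdrawn.
- The Schedule of Activities (footnote 22 for IV, 23 for SC) says: "At least 28 days, and no more than 35 days, after discontinuation of treatment, patients will return to obtain these assessments". It continues: "Subsequent to the Follow-Up visit, patients should be contacted by telephone every 8 weeks", for up to two years. Section 6.3 repeats both.

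None of these general rules exempts a patient who stopped for QTcF or pregnancy.

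In the SAP (6.3.1), OS is a Kaplan-Meier analysis in the ITT set, with missing data censored at the last visit.

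**The concern.** A site facing one of these events can follow the specific rule and close the patient's participation, or follow the general rules and keep the patient in follow-up. Both are defensible on the text, so the same event can be handled in two ways.

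Under the literal reading, the patient loses the Follow-Up visit and the survival calls without having refused anything. For a Part 2 patient, OS is then censored near the time of removal. Survival data that were never collected cannot be recovered at the analysis stage, so this has to be settled in the Protocol rather than the SAP.

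**Working it through.** The plan gives no figure to reproduce here. The check is mainly a comparison of texts.

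**1. Can study simply mean treatment?**
- In 7.1.1, no. The sentence names withdrawal from treatment and then, separately, withdrawal from the study.
- In 7.1.6, possibly. Section 5.4.8 says first-cohort patients needing more than one dose reduction leave the study. It then says that patients over the reduction limit, including the limit of 1 for the first cohort, stop treatment and go into follow-up. The Protocol therefore uses the word loosely at least once.

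**2. Do the general rules cover these patients?** Yes. Unacceptable toxicity and pregnancy sit on the treatment list in 6.4, and 6.3 starts its clock at treatment discontinuation. Both lists in 6.4 are introduced as things that may be included, so they are not exhaustive and do not settle the matter alone.

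**3. What is protected elsewhere?**
- Adverse events: followed for 28 days after the last dose or until drug-related toxicity resolves, whichever is later, or less if new anticancer therapy starts (Schedule footnote 18 for IV, 19 for SC).
- Serious adverse events and deaths: reported through 28 days after the last dose (8.2).
- Pregnancy: followed to its outcome (8.10).
- PFS: essentially unaffected. Scans stop at permanent treatment discontinuation (7.4), and SAP Appendix 1 censors at the last assessment before discontinuation.

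That leaves the Follow-Up visit itself and the survival calls.

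**4. What one removed patient loses.** Assume the two-year limit is 104 weeks from Cycle 1 Day 1, and that the Follow-Up visit falls 4 or 5 weeks after stopping. The maximum number of calls is (104 − week of Follow-Up visit)/8, rounded down.

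| Stop at week | Follow-Up visit at week | Calculation | Maximum calls |
|---|---|---|---|
| 3 | 7 or 8 | 97/8 or 96/8 | 12 |
| 6 | 10 or 11 | 94/8 or 93/8 | 11 |
| 12 | 16 or 17 | 88/8 or 87/8 | 11 or 10 |
| 24 | 28 or 29 | 76/8 or 75/8 | 9 |

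The most that is lost is one visit and 9 to 12 calls, and fewer if the patient dies earlier.

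**5. Chance that a death goes uncounted.** The documents give no expected OS. Assume it is exponential with a median M of 6 to 12 months, and that the patient is alive on stopping at week s, with the Follow-Up visit f weeks later. The probability that death falls after the Follow-Up visit and before week 104 is 2^(−f/M) − 2^(−(104−s)/M), with M in weeks.
- M = 26.1, s = 3, f = 4: 0.899 − 0.068 = 0.83.
- M = 52.2, s = 24, f = 5: 0.936 − 0.346 = 0.59.

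So a removed patient's death would more likely than not be missed. One patient is 1/20 = 5% to 1/10 = 10% of a Part 2 indication (10 to 20 patients, Protocol 9.3).

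**6. How often?** The documents give no rate for either event. With no such patient, the effect is zero.

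**The case against.** The strongest reply is that the general rules already answer the question. Follow-up runs from treatment discontinuation whatever the reason. If refusing visits does not end survival contact, a QTcF reading was hardly meant to. Section 5.4.3 likewise allows dosing to stop after hypersensitivity while the patient stays under follow-up to the end of the study. Section 6.4, on missed visits, adds: "In any circumstance, every effort should be made to document patient outcome, if possible". Section 6.3 says: "Patients continuing to experience toxicity at this point following discontinuation of treatment will continue to be followed at least every 4 weeks". Pregnancy will also be rare, since patients must use two highly effective contraceptive methods and are tested every cycle.

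Most of this stands. It makes the milder reading of 7.1.6 plausible and the practical effect small. It does not repair 7.1.1, whose wording leaves no room for the milder reading.

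A second reply also stands: leaving the study spares a pregnant patient the End of Treatment procedures, which can include CT and a biopsy. Any rewording has to preserve that.

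A reader might infer that 5.4.7 directly contradicts the 2-week QTcF trigger. It does not. Section 5.4.7 requires permanent treatment discontinuation when an interruption for toxicity exceeds 14 days; removal from the study includes that, and 5.4.7 says nothing about follow-up. A reader might also infer that safety follow-up is lost, but the adverse-event, serious-adverse-event and pregnancy rules continue to apply.

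**Conclusion.** The inconsistency is real. It is clear for pregnancy in 7.1.1 and a matter of ambiguous wording for QTcF in 7.1.6. Taken literally, both rules end survival contact for no stated purpose.

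The consequence is small. OS is a secondary endpoint for Part 2 only (Protocol 2.2), the SAP tests no hypotheses (5.1), and the number of affected patients is unknown and may be none. The call counts rest on the assumed start of the two-year limit, and the 0.59 to 0.83 range on the assumed OS.

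It is tempting to go further and say that median OS would be biased by some stated amount, or that the censoring would be informative. The documents do not support either. They give no event rate, no expected OS and no link between these events and prognosis, so neither the direction nor the size of a bias can be derived.

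This is a free improvement of low priority.

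**What to change.** - **7.1.1 and 7.1.6:** replace withdrawal or removal from the study with: *permanently discontinued from study treatment and entered into follow-up (Follow-Up visit, toxicity follow-up to resolution, survival contact) unless consent is withdrawn*.
- **7.1.1:** add a cross-reference to 8.10, and state that study CT and biopsy are not performed in pregnant patients.
- **5.4.8:** change the first-cohort sentence to *discontinued from treatment*, so that it agrees with the sentence after it.

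The QTcF limits and the treatment-stopping criteria stay as they are. The cost is an edit to three sections. The Follow-Up visit and the survival calls already exist, so nothing is added to the schedule, and the SAP needs no change.
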